		9.4.1.1 Primary Efficacy Endpoint (HBsAg
		Seroclearance 24 Weeks After Completion
		of Consolidation Phase Treatment)
		9.4.1.2 Secondary and Exploratory Efficacy
		Endpoints
		9.4.3 Other Analyses
		9.5 Interim Analyses

Amendment /		
Description of Change	Brief Rationale	Section Number and Name
		10.1 Appendix 1: Abbreviations and
		Definitions of Terms
		10.5 Appendix 5: Rash Management
		10.6 Appendix 6: Intervention-emergent
		ALT/AST Elevations
		10.15 Appendix 15: COVID-19 APPENDIX
Race (Asian versus non-Asian)	To provide a reasonably	1.1 Synopsis
was included as a new	balanced representation of race	4.1 Overall Design
stratification factor for	and HBV genotypes across the	4.2 Scientific Rationale for Study Design
participants in Cohort 2.	2 intervention arms of Cohort	6.3 Measures to Minimize Bias:
	2.	Randomization and Blinding
		9.4.1 Efficacy Analyses
		9.4.1.1 Primary Efficacy Endpoint (HBsAg
		Seroclearance 24 Weeks After Completion
		of Consolidation Phase Treatment)
		9.4.1.2 Secondary and Exploratory Efficacy
		Endpoints
The ALT cut off for inclusion	As for some patients the reason	1.1 Synopsis
(criterion A03) was updated	for screen failure was a slight	2.1 Study Rationale
from normal ALT to ALT <2x	and transient elevation of ALT,	4.1 Overall Design
ULN.	experts in the field have	4.2 Scientific Rationale for Study Design
OLIV.	recommended to include	5.1 Inclusion Criteria
	patients with ALT up to ≤2x	3.1 metasion enteria
	ULN.	
ALT elevations were added as	To provide additional guidance	2.3.2.1 Known Risks
a potential risk and the section	on measures to further protect	2.3.2.2.1 Potential Risks for JNJ-3989
on management of ALT	the safety of participants	2.3.3 Benefit-Risk Assessment for Study
elevations was updated.	during treatment with JNJ-	Participation
cievations was apaated.	3989, based on emerging data	8.3.6.2 Intervention-emergent ALT/AST
	from studies REEF-1 and	Elevations
	REEF-D.	10.6 Appendix 6: Intervention-emergent
	KLLI-D.	ALT/AST Elevations
The nonclinical background	For completeness	2.2.1.3.2 Combination of JNJ-3989 with
was updated.	1 or completeness	PegIFN-α2a
was apaated.		2.3.3 Benefit-Risk Assessment for Study
		Participation
Text was added on dose	For completeness	1.1 Synopsis
modifications for PegIFN-α2a.	For completeness	6.1 Study Intervention(s) Administered
modifications for regir n-u2a.		6.6 Dose Modification
		7.1 Discontinuation of Study Intervention
Update of follow-up	For clarification	4.2 Scientific Rationale for Study Design
procedures and criteria for re-	For Clarification	
initiation of NA treatment.		6.6.2 NA Re-treatment Criteria During
mination of NA treatment.		Follow-up
		10.16 Appendix 16: NA Re-treatment
A study intervention	For completeness	During Follow-up 7.1 Discontinuation of Study Intervention
A study intervention discontinuation criterion was	For completeness	7.1 Discontinuation of Study Intervention
added for participants who withdraw consent.		
	For also faction	7.1 Discontinuation of Stude Leterment's
Study intervention	For clarification	7.1 Discontinuation of Study Intervention
discontinuation criteria on		8.3.6.3 Renal Complications

Description of Change	Brief Rationale	Section Number and Name
hepatic decompensation and		
eGFR cr abnormality were		
updated.		
Guidance was included for	For completeness	7.1 Discontinuation of Study Intervention
participants with confirmed		
HBV virologic breakthrough,		
on continuation of study		
treatment and on additional		
sample collection for viral		
sequencing.		
Language was added on data	For completeness	8.10 Medical Encounters
collection for medical		
encounters.		
Language on urine pregnancy	To provide additional guidance	10.15 Appendix 15: COVID-19 APPENDIX
testing for at-home use during	on urine pregnancy testing at	
the COVID-19 pandemic was	home.	
updated.		
Guidance on source data	To provide additional guidance	10.15 Appendix 15: COVID-19 APPENDIX
verification/monitoring and site	on source data	
audits during the COVID-19	verification/monitoring and	
pandemic was added.	site audits.	
Exclusion criterion A01 (M01)	For clarification	5.2 Exclusion Criteria
concerning evidence of HIV-1		
or HIV 2 infection at screening		
and exclusion criterion A06		
(M06) concerning laboratory		
abnormalities at screening was		
updated.		
It was clarified that JNJ-3989	For clarification	1.1 Synopsis
should preferably be		6.1 Study Intervention(s) Administered
administered via subcutaneous		
injection in the abdomen		
Head, neck, and thyroid were	For completeness.	8.2.1 Physical Examinations
added to complete physical		
examination.		
Management of rash and acute	For correction and clarification	8.3.6 Adverse Events of Special Interest
systemic allergic reactions	as rash and acute systemic	8.3.7 Other Toxicities
were moved under a separate	allergic reactions are not	
subheader.	considered AESIs for JNJ-	
	3989 or JNJ-6379.	
Minor errors were corrected	Correction and clarification.	Throughout the protocol
and minor clarifications were		
made.		

## Amendment 4 (30 April 2021)

Overall Rationale for the Amendment: The primary reason for this amendment is to add guidance on the concomitant use of COVID-19 vaccines and PegIFN- $\alpha$ 2a.

Description of Change	Brief Rationale	Section Number and Name
-----------------------	-----------------	-------------------------

Guidance was added on the	Due to overlapping safety	6.5 Concomitant Therapy
concomitant use of COVID-19	profiles of PegIFN-α2a and	10.15 Appendix 15: COVID-19 APPENDIX
vaccines and PegIFN-α2a	COVID-19 vaccines	
A liver ultrasound will be done	As per standard practice for the	1.3.1 Schedule of Activities – Screening
yearly for all participants and	monitoring of patients with	Phase and Induction Phase
remains recommended every 6	chronic HBV infection	1.3.2 Schedule of Activities – Consolidation
months for high-risk		Phase and Follow-up Phase
populations		
The demographics of the	To better align with the	
African/African American	AASLD guidelines	
population considered at high-	3	
risk for developing HCC and		
who fall under 6-monthly liver		
ultrasound screening are		
further specified		
Language on urine pregnancy	To provide additional guidance	1.3.2 Schedule of Activities – Consolidation
testing for at-home use was	on urine pregnancy testing at	Phase and Follow-up Phase
updated	home	wp I mad
Minor corrections were made	Correction	1.3.2 Schedule of Activities – Consolidation
were made	Concensi	Phase and Follow-up Phase
		i nase and i onow-up i nase

#### Amendment 3 (26 January 2021)

**Overall Rationale for the Amendment:** The primary reason for this amendment is to increase the upper age limit for participant inclusion from 45 years to 55 years and to allow participants who received <9 months of NA treatment if not within 12 months prior to screening. In addition, other changes and minor clarifications and corrections were made as detailed below.

Description of Change	Brief Rationale	Section Number and Name
Upper age limit for inclusion	Typically, CHB patients with	1.1 Synopsis
was changed from 45 years to	high HBV DNA and normal	4.1 Overall Design
55 years with a maximum of	ALT are relatively young.	5.1 Inclusion Criteria
approximately 10 participants	However, in practice older	
$>45$ to $\leq 55$ years of age.	patients up to 55 years of age	
	are still seen in this stage of	
	CHB.	
In addition to NA treatment	If the requirements for HBV	1.1 Synopsis
naïve participants, participants	DNA and ALT are met at study	2.1 Study Rationale
who have received <9 months	entry, no relevant impact of	4.1 Overall Design
of NA treatment ≥12 months	prior short-term NA treatment is	5.1 Inclusion Criteria
prior to screening (eg, during	expected.	
pregnancy to prevent mother-		
to-child-transmission) are also		
allowed.		
Exclusion criterion A25 e was	The black or African American	5.2 Exclusion Criteria
updated to include a separate,	population generally has lower	
lower ANC cut off for black or	ANC values compared with	
African American participants.	other populations.	
The exclusion criterion on	This criterion only applies to	5.2 Exclusion Criteria
CD4+ cell count was removed.	HBV/HIV coinfected patients	
	who are excluded from	
70 777 60 70 1 11	participation in this study.	
If JNJ-6379 is discontinued,	Discontinuation of JNJ-6379	7.1 Discontinuation of Study Intervention
participants may continue JNJ-	does not necessarily lead to	
3989 (and PegIFN-α2a if		

Description of Change	Brief Rationale	Section Number and Name
applicable) after discussion with the sponsor.	discontinuation of JNJ-3989 (and PegIFN-α2a if applicable).	
Anticoagulants were moved from the list of disallowed medications to the list of concomitant medications to be used with caution.	Preclinical and clinical data for JNJ-3989 and JNJ-6379 do not show evidence of coagulopathy.	6.5 Concomitant Therapy
Nonclinical data on the combination of JNJ-3989 or JNJ-6379 with PegIFN-α2a were added.	These data confirm that JNJ-3989 or JNJ-6379 in combination with PegIFN-α2a is well tolerated.	2.2.1.3.1 Combination of JNJ-6379 with PegIFN-α2a 2.2.1.3.2 Combination of JNJ-3989 with PegIFN-α2a 2.2.2.3 Combination of JNJ-3989 and JNJ-6379 with PegIFN-α2a 2.3.3 Benefit-Risk Assessment for Study Participation
Cystatin C was added to the blood chemistry panel.  PK information on the combination of TDF with JNJ-6379 was added.	Clinical study data suggest increased tenofovir plasma concentrations when given in combination with JNJ-6379. Therefore, additional renal monitoring by means of cystatin C testing was added to the protocol.	2.2.2.2 Combination of JNJ-3989 and JNJ-6379 with Tenofovir Disoproxil 10.2 Appendix 2: Clinical Laboratory Tests
The potential for JNJ-6379 to increase tenofovir plasma concentrations was added to the potential risks.	Clinical study data suggest increased tenofovir plasma concentrations when given in combination with JNJ-6379.	2.3.2.2.3 Potential Risks for Tenofovir Disoproxil and PegIFN-α2a
A footnote was added to exclusion criteria 2 a, b, c and d to clarify that bilirubin, prothrombin time and serum albumin above or below the cut off are exclusionary unless they can be explained by anything other than hepatic decompensation.	Clarification	5.2 Exclusion Criteria
Minor errors were corrected.	Correction	1.3.1 Schedule of Activities – Screening Phase and Induction Phase 1.3.2 Schedule of Activities – Consolidation Phase and Follow-up Phase 6.1 Study Intervention(s) Administered 6.2 Preparation/Handling/Storage/Accountability 6.6.1 Study Intervention Completion at Consolidation Week 12 8.3 Adverse Events, Serious Adverse Events, and Other Safety Reporting 8.3.6.5 Hematologic Abnormalities 10.4 Appendix 4: Adverse Events: Definitions and Procedures for Recording, Evaluating, Follow-up, and Reporting 10.11 Appendix 11: Hepatitis B Quality of Life Instrument

## **Amendment 2 (08 July 2020)**

Overall Rationale for the Amendment: The protocol was amended as specified below

Description of Change	Brief Rationale	Section Number and Name
The COVID-19 appendix was updated to include details on home health visits performed by a nurse	To allow visits to be performed by a nurse at the participant's home (following the schedule of activities as closely as possible) in case of restrictions due to the COVID-19 pandemic	10.15 Appendix 15: COVID-19 APPENDIX
All references to blinding/unblinding in the COVID-19 appendix were removed	Minor corrections	10.15 Appendix 15: COVID-19 APPENDIX
Other clarifications and additions made to the COVID-19 appendix		10.15 Appendix 15: COVID-19 APPENDIX
Correct position of footnote 'h'		1.3.1 Schedule of Activities – Screening Phase and Induction Phase
Footnote 'r' was corrected to ensure the Day-1 ECG will be collected and assessed locally		1.3.1 Schedule of Activities – Screening Phase and Induction Phase
Exclusion criterion M04 should reference criterion M02.1 instead of A02a		5.2 Exclusion Criteria

## Amendment 1 (24-April-2020)

**Overall Rationale for the Amendment:** Following Health Authority (HA) feedback the protocol was amended as specified below

Description of Change	Brief Rationale	Section Number and Name
TSH and T4 testing were added at screening, end of induction phase, and end of consolidation phase	To ensure participants meet eligibility criteria related to thyroid function and to ensure thyroid function is monitored as per the PegIFN-α2a prescribing information	1.3.1 Schedule of Activities – Screening Phase and Induction Phase 1.3.2 Schedule of Activities – Consolidation Phase and Follow-up Phase 10.2 Appendix 2: Clinical Laboratory Tests
It was added that participants with a decrease or loss of vision will have a prompt and complete ophthalmic examination during induction and consolidation phase	Given the known ophthalmologic toxicities of PegIFN-α2a, ophthalmic examinations will be continued through the consolidation phase as indicated	1.3.1 Schedule of Activities – Screening Phase and Induction Phase 1.3.2 Schedule of Activities – Consolidation Phase and Follow-up Phase
Exclusion criterion A25 was amended to exclude participants with depression or psychiatric disorders that are not adequately controlled on a stable medication regimen	To be consistent with the PegIFN- α2a prescribing information	5.2 Exclusion Criteria
Criteria were added for discontinuation of treatment with PegIFN-α2a	In line with the PegIFN-α2a prescribing information	7.1 Discontinuation of Study Intervention
The discontinuation criterion related to disallowed medication was updated	In line with the list of disallowed medications in Table 3	7.1 Discontinuation of Study Intervention
Contraindications for PegIFN-α2a treatment assessed at screening will need to be re-assessed at the end of	For completeness	1.3.1 Schedule of Activities – Screening Phase and Induction Phase

Description of Change	Brief Rationale	Section Number and Name
the induction phase prior to randomization (i.e., prior to start of PegIFN-α2a treatment)		5.2 Exclusion Criteria
Additional details on handling missing data were added to the protocol	For completeness	9.4.1.1 Primary Efficacy Endpoint (HBsAg Seroclearance 24 Weeks After Completion of Consolidation Phase Treatment) 9.4.1.2 Secondary and Exploratory Efficacy Endpoints
Information on the confidence level used for sample size calculation was added	For completeness	1.1 Synopsis 9.2 Sample Size Determination
Additional details on the analysis of the primary endpoint were added	For completeness	9.4.1.1 Primary Efficacy Endpoint (HBsAg Seroclearance 24 Weeks After Completion of Consolidation Phase Treatment)
Additional details were added on who will have access to the interim analysis results	For completeness	1.1 Synopsis 9.5 Interim Analyses
Liver biopsy result within 1 year prior to screening (instead of 2 years prior to screening) or at the time of screening is allowed for eligibility	For consistency with the inclusion criteria	1.3.1 Schedule of Activities – Screening Phase and Induction Phase
Guidance on study conduct during the COVID-19 pandemic was added	Options for study-related participant management are being provided in the event of disruption to the study conduct due to the COVID-19 pandemic.	1.3 Schedule of Activities 10.15 Appendix 15: COVID-19 APPENDIX
Minor errors were corrected	Correction	Title Page and footer 2.2.2.1 JNJ-3989 and JNJ-6379 2.2.2.2 Combination of JNJ-3989 and JNJ-6379 with Tenofovir Disoproxil

# 10.15. Appendix 15: COVID-19 APPENDIX GUIDANCE ON STUDY CONDUCT DURING THE COVID-19 PANDEMIC

This appendix applies to all current approved versions of protocol 73763989PAHPB2005.

It is recognized that the Coronavirus Disease 2019 (COVID-19) pandemic may have an impact on the conduct of this clinical study due to, for example, self-isolation/quarantine by participants and study site personnel; travel restrictions/limited access to public places, including hospitals; study site personnel being reassigned to critical tasks.

In alignment with recent health authority guidance, the sponsor is providing options for study-related participant management in the event of disruption to the conduct of the study. This guidance does not supersede any local or government requirements or the clinical judgement of the investigator to protect the health and well-being of participants and site staff and maintain oversight of delegated trial activities. If, at any time, a participant's safety is considered at risk, study intervention will be discontinued, and study follow-up will be conducted.

Scheduled visits that cannot be conducted in person at the study site will be performed to the extent possible remotely/virtually or delayed until such time that on-site visits can be resumed. At each contact, participants will be interviewed to collect safety data. Key efficacy endpoint assessments should be performed if required and as feasible. Participants will also be questioned regarding general health status to fulfill any physical examination requirement.

Every effort should be made to adhere to protocol-specified assessments for participants on study intervention, including follow up. Modifications to protocol-required assessments may be permitted via COVID-19 Appendix after consultation with the participant, investigator, or the sponsor. Missed assessments/visits will be captured in the clinical trial management system for protocol deviations. Discontinuations of study interventions and withdrawal from the study should be documented with the prefix "COVID-19 related" in the CRF.

The sponsor will continue to monitor the conduct and progress of the clinical study, and any changes will be communicated to the sites and to the health authorities according to local guidance. If a participant has tested positive for COVID-19, the investigator should contact the sponsor's responsible medical officer to discuss plans for study intervention and follow-up. Modifications made to the study conduct as a result of the COVID-19 pandemic should be summarized in the clinical study report.

#### **GUIDANCE SPECIFIC TO THIS PROTOCOL**

The following emergency provisions are meant to ensure participant safety on study while site capabilities are compromised by COVID-19-related restrictions. Remote medical consultation and alternatives to study intervention dispensing, administration, and clinical laboratory assessments may allow continued study participation for participants in this trial. Before implementing any of these emergency provisions, the sponsor should be consulted to perform a benefit-risk analysis and to ensure the measures are executed and documented correctly.

As restrictions are lifted and the acute phase of the COVID-19 pandemic resolves, sites should revert to original protocol conduct as soon as feasible and in accordance with any country-specific regulatory requirements.

#### Screening and randomization:

Enrollment of new participants may continue based on the investigator's assessment of risks versus benefits, depending on the situation at a particular site, and the ability to monitor participant safety.

Baseline visits for participants recently screened for this study should be postponed if the current situation does not allow for an orderly conduct of the study.

#### Dispensing/administration of study intervention:

- For participants unable to visit the study site, direct-to-patient (DTP) shipment or handover to a caregiver or delegate of oral study intervention may be implemented, where allowed per local regulations and if requested by the treating study physician. Where DTP shipments or handover to delegates are deemed necessary, the process must be coordinated between the site and sponsor staff following standard DTP procedures for arranging shipment and adhering to associated approvals and documentation requirements.
- For participants able to visit the study site, but who request to reduce visit frequency, or for whom limited access to the site is expected, an additional supply of oral study intervention can be provided.
- JNJ-3989 should be administered by a nurse at the study site or, if this is not possible, at the participant's home. Of note, if a scheduled injection of JNJ-3989 is not possible, the injection should be given as soon as possible within 3 weeks after the scheduled time.

#### **Continuation of study intervention:**

- Any issue with continuation of study intervention should be discussed with the sponsor and well documented.
- Study intervention should be continued if, in the assessment of the investigator, it does not result in risk to the participant. If at any time a participant's safety is considered at risk due to study intervention, study intervention will be temporarily or permanently discontinued, while every effort should be made to maintain follow-up on study. The benefit of continuing study intervention should be assessed by the investigator for each individual participant, considering the potential impact of reduced direct clinical supervision on participant safety.

- Amendment 7
- If a participant develops a COVID-19 infection, the investigator should contact the sponsor to discuss plans for study intervention and follow-up. A decision to continue study intervention should be made by the investigator depending on symptoms and concomitant medication used for the treatment of COVID-19. Study intervention must be discontinued if prohibited medication is used.
- When a participant, for whom study intervention has been interrupted, recovers from suspected or confirmed SARS-CoV-2 infection or related disease and all AEs related to SARS-CoV-2 infection improve to Grade ≤1, the investigator should discuss with the sponsor about resuming study intervention.

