## Study interventions:

- Prior to Protocol Amendment 6: The term "study intervention" throughout the protocol, refers to JNJ-3989, JNJ-6379, NA and pegylated interferon alpha-2a (PegIFN-α2a).
- As of Protocol Amendment 6: The term "study intervention" throughout the protocol, refers to JNJ-3989, NA and PegIFN-α2a.

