#### Disallowed from 6 months prior to baseline until end of follow-up:

• Any systemically (eg, intravenously, intramuscularly, orally, subcutaneously) administered medication that directly or indirectly interferes with immune responses (eg, cyclosporine, interleukins, programmed death-[ligand] 1 inhibitors, systemic corticosteroids exceeding 5 mg of prednisolone equivalent/day).

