# 7.1. Discontinuation of Study Intervention

With the implementation of Protocol Amendment 6, all participants had to stop JNJ-6379 treatment immediately.

Treatment with JNJ-3989 and PegIFN- $\alpha$ 2a must be discontinued before consolidation Week 12 for all reasons listed in Section 7.1 of the Master Protocol PLATFORMPAHPB2001 and for all additional intervention-specific reasons. All the discontinuation criteria are listed below and the intervention-specific criteria are highlighted (colored fill). For the few criteria from the Master

Protocol that are specified or more restricted in this ISA, the changes compared to the Master Protocol are also highlighted (colored fill). If JNJ-3989 is discontinued, PegIFN- $\alpha$ 2a should also be discontinued. If PegIFN- $\alpha$ 2a is discontinued, JNJ-3989 should be continued. NA treatment may be continued or, in consultation with the sponsor, discontinued based on investigator judgement.

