#### 8.3.7.1. Rash

Participants should be informed that they should contact their doctor immediately when they notice any generalized skin reaction. This skin reaction should be evaluated in the clinic the same day (if possible) or the next possible day.

All rash events should be captured in the AE section of the CRF. Separate Rash pages will be completed in case of a rash event.

Monitoring of the evolution of rash events will be performed as described in Table 6 in Section 10.5, Appendix 5, Rash Management.

When safety blood samples are drawn as per the rash management guidelines, these should be processed by the local laboratory. The following parameters will need to be tested: AST, ALT, sedimentation rate, complete blood cell count (including hemoglobin, hematocrit, RBC count, WBC count, differential count [neutrophils, lymphocytes, monocytes, eosinophils, and basophils], and platelet count), and creatinine. The values of the local laboratory assessments need to be transcribed in the CRF by the study site personnel.

The participant may be treated symptomatically until the rash resolves. Oral antihistamines (eg, cetirizine, levocetirizine) and/or topical corticosteroids may provide symptomatic relief but effectiveness of these measures has not been established. If systemic corticosteroids exceeding 5 mg of prednisolone equivalent/day are required for treatment of rash, JNJ-3989 and PegIFN- $\alpha$ 2a need to be permanently discontinued. NAs can be continued. If the rash is considered to be most likely due to concomitant illness or non-study drugs, standard management, including discontinuation of the likely causative agent, should be undertaken.

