#### **Definitions of Terms**

ALT/AST nadir Lowest ALT/AST value during study participation

End-of-study intervention

(EOSI)

Time of the last administration of study intervention

HBsAg seroclearance HBsAg negativity based on the assay used

HBsAg seroconversion HBsAg negativity and anti-HBs antibody positivity

Intervention cohort Cohorts of adult participants with chronic hepatitis B virus infection who receive a

specific study intervention within this Platform study, and in whom the efficacy and

safety of that intervention is evaluated

Study intervention Prior to Protocol Amendment 6: JNJ-73763989, JNJ-56136379, NA (tenofovir

disoproxil) and PegIFN-α2a

As of Protocol Amendment 6: JNJ-73763989, NA (tenofovir disoproxil) and

PegIFN-α2a

Study intervention phase 36-week induction phase plus 12-week consolidation phase

Virologic breakthrough Confirmed on-treatment HBV DNA increase by >1 log10 IU/mL from nadir or

confirmed on-treatment HBV DNA level >200 IU/mL in participants who had HBV

DNA level <LLOQ of the HBV DNA assay

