#### Study visits and assessments:

- If possible, central laboratory testing as outlined in the Schedule of Activities is to be continued. If central laboratory tests cannot be performed, the use of a local laboratory is allowed for study evaluations. A copy of the local laboratory report should be reviewed by the investigator and filed with the source documents, along with reference ranges.
- To safely maintain participants on study intervention while site capabilities are compromised by COVID-19-related restrictions, study visits may be performed by a nurse (who received study-specific training) at the participant's home (home health visits) until such time that on-site visits can be resumed. The following activities may be completed as required per the Schedule of Activities and as feasible:

- Sampling, processing and shipping of laboratory samples (as described above)
- Checking study compliance: medication diary (if available), intake of oral study intervention, storage of oral study intervention
- Performing ECGs
- Collecting participant-reported outcomes (where appropriate translations and licensing are available)
- If JNJ-3989 is administered at the participant's home, it will need to be done by a nurse (who received study-specific training)
- Delivering oral study interventions and urine pregnancy tests for at-home use
- Any data related to adverse events, concomitant medication, vital signs, and ECGs will be reviewed and assessed by the investigator.
- In addition, participants may have tele-health visits conducted by qualified site personnel via phone or video conversation as per local regulation. Assessments may include review of adverse events (including injection site reactions), concomitant medications, and study intervention accountability. Participants will also be questioned regarding general health status to fulfill any physical examination requirement. Patient-reported outcomes may be collected (where appropriate translations and licensing are available) following the Site Assisted Administration Process Guidance.
- Procedures and timings should follow the Schedule of Activities as closely as possible. Standard Adverse Event/Serious Adverse Event reporting requirements apply.

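### Appendix 15's COVID-19 rule on prohibited medication also stops NA, which Section 7.1 and the toxicity rules never mandate

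*Protocol*

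**What the plan says.** Protocol Appendix 15 (Section 10.15), in its part on continuing study intervention, deals with a participant who develops COVID-19. The investigator contacts the sponsor and decides on continuation in the light of symptoms and of the drugs given for COVID-19. A flat rule follows: "Study intervention must be discontinued if prohibited medication is used".

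The term is defined. The Synopsis and Section 2 state that, as of Amendment 6 and throughout the protocol, it "refers to JNJ-3989, NA and PegIFN-α2a". Appendix 1 repeats this ("As of Protocol Amendment 6: JNJ-73763989, NA (tenofovir disoproxil) and" PegIFN-α2a). Appendix 15 uses the term in the same sense. For participants with limited access to the site, "an additional supply of oral study intervention can be provided", and the home nurse checks "intake of oral study intervention, storage of oral study intervention". With JNJ-6379 removed, NA is the only oral agent left.

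Section 7.1 treats the agents separately. JNJ-3989 and PegIFN-α2a must stop when a listed criterion is met, whereas "NA treatment may be continued or, in consultation with the sponsor, discontinued based on investigator judgement".

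Table 3 in Section 6.5 gives the disallowed medication. It includes "systemic corticosteroids exceeding 5 mg of prednisolone equivalent/day", and each of its four groups runs to the end of follow-up.

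**The concern.** Read with the protocol's own definition, the Appendix 15 sentence orders NA to be stopped whenever prohibited medication is used during COVID-19, whether or not the NA completion criteria have been met. Elsewhere the protocol takes care that NA is not withdrawn casually. Section 4.2 explains that the completion criteria were chosen so that only participants with a chance of a sustained off-treatment response stop everything. Section 2.3.2.2 names NA discontinuation as a risk for hepatitis B flares. Section 4.2 reports that monitoring and re-treatment rules were tightened after a severe flare following NA discontinuation in the REEF-2 control arm. Section 2.3.3 refers to a further update prompted by a post-treatment reactivation with subacute hepatic failure.

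A site that follows the sentence literally would take NA away from HBeAg-positive participants who were meant to stay on it. It would do so without the four laboratory conditions that otherwise have to be met first.

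**Working it through.** There is no stated figure to reproduce. The check sets the rules side by side.

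**1. What each early stop rule says about NA**

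| Protocol section | NA instruction | Mandates stopping NA? |
|---|---|---|
| 7.1, general criteria | May continue; may be stopped on judgement with the sponsor | No |
| 8.3.6.2, ALT/AST elevations | Should continue | No |
| 8.3.6.3, renal | Tenofovir disoproxil switched to TAF | No |
| 8.3.6.4, hematologic | Should continue | No |
| 8.3.7.1, rash | Can continue | No |
| 8.3.7.2, allergic reactions | May be stopped on judgement with the sponsor | No |
| Appendix 15, prohibited medication in COVID-19 | Included in study intervention, no exception | Yes |

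Mandatory NA stop in the first six rows: 0 of 6. Explicit should or can continue: 8.3.6.2, 8.3.6.4 and 8.3.7.1, so 3 of 6.

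**2. The same drug under two rules**

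The steroid listed in Table 3 is also the trigger in the rash section: "If systemic corticosteroids exceeding 5 mg of prednisolone equivalent/day are required for treatment of rash", then JNJ-3989 and PegIFN-α2a stop and NA can continue. Counting the agents stopped out of the agents being given:

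| Phase | Agents given | Rash rule stops | Appendix 15 stops |
|---|---|---|---|
| Induction | JNJ-3989, NA | 1 of 2 | 2 of 2 |
| Consolidation | JNJ-3989, NA, PegIFN-α2a | 2 of 3 | 3 of 3 |
| Follow-up, still on or back on NA | NA | 0 of 1 | 1 of 1 |

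In every row the difference is exactly one agent, NA.

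**3. Follow-up**

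- Table 3 still applies.
- Footnote f of the follow-up Schedule of Activities (Section 1.3.2) says that JNJ-3989 and PegIFN-α2a are no longer given. NA is dispensed only to participants who could not stop it or who met re-treatment criteria.
- Section 7.1 frames its mandatory criteria as discontinuation before consolidation Week 12, so it does not govern here.
- Section 6.6.1 says that participants who miss the completion criteria should stay on NA for the 48 weeks. Section 6.6.2 says when NA should be restarted.
- The only thing the Appendix 15 sentence can stop in this phase is therefore the NA that Sections 6.6.1 and 6.6.2 call for.
- Footnote d of the same schedule lets these participants skip FU Weeks 8, 16, 20, 28, 32, 40 and 44 while HBV DNA and ALT are stable. Some may therefore be on the lighter visit schedule when NA is withdrawn.

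**4. Rules that do stop NA**

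- Section 6.6.1 stops NA at FU Week 2, as planned completion, once HBsAg, HBeAg, HBV DNA and ALT all meet their limits.
- Two sentences in Appendix 15 discontinue study intervention when a participant's safety is judged to be at risk. By definition these reach NA too, but they depend on an assessed risk.

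Neither is triggered by use of a prohibited drug, so neither conflicts with Section 7.1 or the toxicity sections.

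**The case against.** The strongest reply is that the protocol does not always use the term strictly. Section 7.1 is headed as discontinuation of study intervention, yet its mandatory part covers only JNJ-3989 and PegIFN-α2a. Appendix 1 defines the end of study intervention as its last administration, while the schedule places that visit at consolidation Week 12, although NA runs to at least FU Week 2. A site might therefore turn to Section 7.1 and find NA handled sensibly. This makes it likely that only two agents were meant. It does not settle the matter, because Section 7.1 gives no cover in follow-up and Appendix 15 itself counts NA in the term.

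Second, the sentence is surrounded by safeguards. The investigator contacts the sponsor, the sponsor is consulted before emergency provisions are used, the appendix does not override clinical judgement, and resumption after recovery is to be discussed. These stand as reasons why harm is unlikely. None exempts NA, and the mandatory wording comes straight after the sentence that gives the investigator discretion.

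Third, the steroid comparison is not fully like for like: the rash rule is permanent, while Appendix 15 foresees resumption. That is correct, so the comparison shows scope only. The general rule for disallowed medication is the criterion in Section 7.1 (at least 7 days needed and no intention to stop the drug), and that too stops only JNJ-3989 and PegIFN-α2a.

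Fourth, Section 6.5 refers to the tenofovir disoproxil prescribing information for further prohibited drugs, and for some of these stopping NA could be right. This stands. A reader might infer that NA should continue whatever the prohibited drug is; the documents do not support that, and the fix allows for it.

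Fifth, Sections 7.1 and 6.5 refer to the Master Protocol, which is not among the documents. Whether it narrows the sentence cannot be checked.

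**Conclusion.** The sentence is wrong as written, with minor severity. It mandates stopping NA where Section 7.1 and the five toxicity sections do not (0 of 6). Compared with the rash rule it adds one agent in every phase, and in follow-up that agent is the only one given.

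Three stronger readings go too far.

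- A reader might infer that nothing else in the plan ever requires NA to stop. Planned completion under Section 6.6.1 does, and the safety-at-risk sentences in Appendix 15 can. These are separate rules.
- A reader might infer that the lack of a 7-day threshold in Appendix 15 is itself an error. A stricter trigger during COVID-19 is a permissible choice.
- A reader might infer that participants were harmed or that the efficacy result is at risk. The documents give no number affected, the safeguards make an unreviewed stop unlikely, and the definition, analysis set and missing-data rules of the primary endpoint do not depend on this sentence.

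The conclusion assumes that the protocol's definition applies in Appendix 15, as the protocol says it does throughout, and that the Master Protocol does not restrict the sentence.

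**What to change.** Replace the Appendix 15 sentence with: *JNJ-3989 and PegIFN-α2a must be stopped if the participant takes prohibited medication; NA should be continued unless the investigator, in consultation with the sponsor, decides otherwise (eg, if the medication is prohibited with tenofovir per its prescribing information).*

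This keeps the strict COVID-19 trigger, agrees with Sections 7.1 and 8.3.7.1, and works in follow-up, where only its second half has any effect. Leave the rest of Appendix 15, Sections 7.1 and 8.3.7.1 and the SAP as they are, and add no duration condition. The cost is one sentence in a protocol amendment, with no new data, visits or procedures and no change to the analysis.
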